3.2.7 Follow-Up Observation Period (All Treatment Pathways)

The End of Treatment visit will be followed by a 12-month observation period. During observation, management of peanut allergy will be guided by the subject's physician.

ARC008 Protocol Amend 6.0

Observation assessments will be conducted by telephone at 3, 6, and 9 months to enquire about the following:

- Current treatment plan (eg, commercially available product, complete peanut avoidance, use of food equivalents for peanut oral immunotherapy, other investigational immunotherapy, other)
- Events of systemic allergic reactions, EoE, accidental/nonaccidental exposures to food allergens and their outcomes, use of epinephrine, hospitalizations (all causes), emergency department visits (all causes), and SAEs

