3.7 Study Discontinuation

Each subject will continue in the study until 1 or more of the following events occurs:

- The risk/benefit profile for the subject to continue in the study is no longer favorable in the opinion of the investigator.
- The investigator withdraws the subject from the study.
- The subject withdraws consent.
- The sponsor discontinues development of AR101 in the relevant participating country.
- Subject completes the End of Treatment visit and the 1-year follow-up observation period.

After one of these events occurs, the subject will return to the clinic for an End of Treatment or Study Exit visit, as appropriate.

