4.4 Early Discontinuation

A subject may discontinue dosing with AR101 anytime if the investigator determines that continuation in the study is detrimental to the subject. Following early discontinuation, subjects will return to the clinic to complete the End of Treatment visit.

Early discontinuation procedures may be affected by a pandemic, epidemic, or other emergency not related to the study as described in Appendix 12.

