4.4.1 Criteria for Early Discontinuation

A subject who meets any of the following must discontinue dosing with AR101:

- 1. Pregnancy
- 2. Life-threatening symptoms (CoFAR grade 4; Appendix 9), including, but not limited to anaphylaxis resulting in hypotension, neurologic compromise, or mechanical ventilation secondary to peanut OIT dosing or any peanut food challenge
- 3. Severe allergic hypersensitivity symptoms (CoFAR grade 3; Appendix 9) that require intensive therapy (to be determined by the investigator but may include such interventions as IV epinephrine, intubation, or admission to an intensive care unit) or those that are recurrent. Subjects who experience severe symptoms (eg, severe nausea, rhinorrhea, or pruritus) that are not life-threatening, not requiring intensive therapy, and not associated with any other features indicating a serious clinical condition, and who the investigator feels are suitable to continue with the study, will be discussed with the medical monitor and may continue the study under close supervision if both the investigator and the medical monitor deem it appropriately safe to do so
- 4. Dose-limiting symptoms that occur at or before the 3 mg single dose on Initial Escalation Day 1 (Treatment Pathways 3 and 5 only)
- 5. Dose-limiting symptoms that occur on Initial Escalation Day 2 (Treatment Pathways 3 and 5 only)
- 6. Nonadherence: For subjects on a daily dose regimen, missing > 7 consecutive dosing days on any 1 occasion or missing 3 consecutive dosing days on 3 or more occasions during Up-Dosing, other than for treatment of an AE or a dispensing error
- 7. Extended dosing interruptions: For subjects on a daily dose regimen, any circumstances, including medical indications that require missed AR101 dosing for ≥ 15 consecutive days, with the exception of the voluntary 30-day hiatus for GI AEs
- 8. On 1 episode, failure to accomplish up-dosing to 300 mg AR101 daily after 3 attempts (Treatment Pathways 2 and 3 only)
- 9. On 1 dose-reduction episode, failure to identify a tolerated dose of AR101 after 3 attempts at dose reduction

- ARC008 Protocol Amend 6.0
- 10. Administration of more than 2 doses of epinephrine for the treatment of any single AR101-related allergic reaction
- 11. Subject desires to receive commercially available product

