- Reducing dose by 1 or 2 dose levels and maintaining the reduced dose level for 2- to 4-week period before attempting dose re-escalation Generally, this should be the action taken when a dose that has been observed at the study site is assessed as not tolerated, if a dose elicits moderately severe symptoms, if a single dose of epinephrine has been administered to treat a dosing reaction, or if the investigator is convinced of the intolerability of the current dose level. In short, it should be considered the default action whenever a dose or dose level is assessed *as not tolerated*.

- Reducing dose level for less than the usual 2-week period this may be instituted as treatment for an intercurrent AE, to aid the investigator in determining if a dose level is or is not tolerated, or if a pattern of decreased study product tolerability during menses is discerned. The level of the reduction in dose, ranging from a 1-step reduction to a 50% reduction will be at the investigator's discretion, based on clinical judgment. The manner in which dose escalation may resume will depend on the level and the duration of the dose reduction.
- Temporarily withholding study product dosing this may be instituted as treatment for an intercurrent AE or to aid the investigator in determining if a dose level is or is not tolerated, but the duration of withholding study product may not exceed 14 consecutive days, or the subject will be discontinued from the study. The manner in which dosing may resume after withholding dosing of study product depends on the duration for which dosing was withheld.
- Reducing dose by 2 dose levels and maintaining the reduced dose level for ≥ 6 weeks – continuing dosing at a reduced dose level for ≥ 6 weeks prior to attempting re-escalation is mandatory if 2 doses of epinephrine are given to treat a single AE.
- Stopping dosing and discontinuing the subject early from the study this is an option that the subject may elect anytime and for any reason. The investigator must discontinue the subject from further dosing and continuation in the study under circumstances that could jeopardize the health of the subject or the integrity of the study.

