The investigator should assess the benefit-risk of continued AR101 treatment when a subject has several AR101-related systemic allergic reactions (anaphylactic events) during maintenance treatment. AE, adverse event; BIW, twice weekly; QD, once daily; QOD, every other day; QOW, every other week; QW, once weekly; SAE, serious adverse event.

- This study period consists of the subject receiving the 300 mg dose of study product QD, QOD, BIW, QW, or QOW. For any noted symptoms during the QD Initial Maintenance or Extended Maintenance period, the same study product dosing guidelines and procedures for QD dosing will be followed as for the Up-Dosing Period. However, for subjects on nondaily regimens, the following guidelines and procedures apply. The investigator should assess the benefit-risk of continued AR101 treatment when a subject has several AR101-related systemic allergic reactions (anaphylactic events) during maintenance treatment.
- The tolerability of doses on nondaily dosing regimens will be evaluated as in Section 6.8 and Table 10. In the event of a clinically significant intercurrent AE occurring at the time of a scheduled QOD, BIW, QW, or QOW dose, subjects should be advised to hold the scheduled dose until the AE is resolved and the dose can be safely administered; the interval between doses should be reset once the subsequent dose is tolerated. *If the dose must be held for > 3 days past when the dose was due to be taken*, the investigator must discuss the case with the sponsor's medical monitor prior to administering the next dose. Options available at that time include, but are not limited to, any of the following:

- ARC008 Protocol Amend 6.0
- 1. Continue the same Treatment Pathway and administer the next 300 mg dose under supervision at the study site.
 - a. If tolerated, continue EM dosing at 300 mg on the same schedule, resetting the dosing interval;
 - b. If not tolerated, consider options 2 or 3 below.
- 2. Continue the same Treatment Pathway and administer approximately half of the 300 mg dose under supervision at the study site. The entire 300 mg dose should be prepared with the preferred vehicle and then approximately half of the dose should be administered; the remainder should be discarded. If not tolerated, the subject should be discontinued from the study. If tolerated, up to 3 successive doses can be administered this way according to the subject's assigned schedule, but then 300 mg should again be attempted.

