8.1.4.2 Gastrointestinal AEs Resulting in Prolonged Interruption of Dosing

Gastrointestinal AEs, typically chronic/recurrent GI AEs, that result in prolonged interruption of dosing will also be considered AEIs and will be assessed longitudinally according to the procedures described below. EoE presents with varied symptoms of esophageal dysfunction that differ between children and adults (Dellon, 2011; Dellon, 2013). In children, the symptoms are often nonspecific and may include feeding difficulties, failure to thrive, abdominal pain, regurgitation, nausea, and vomiting. In adults, the most frequent symptoms are dysphagia and food impaction; less frequent symptoms include heartburn, chest pain, abdominal pain, nausea, or vomiting. Special attention should be paid to these symptoms, which may suggest esophageal dysfunction, particularly when the symptoms are new in onset during the study, chronic or recurrent, or experienced as a complex of multiple symptoms.

To delineate these AEIs, prolonged interruption of dosing is defined as withholding AR101 for > 7 days. This will include 3 categories of subjects:

- Any subject whose dose is withheld for > 7 days due to GI AEs and resumes dosing at a reduced dose level
- Any subject who develops chronic/recurrent GI AEs at or before reaching the 20 mg dose level and resumes dosing after a 30-day dosing hiatus
- Any subject who experienced GI AEs and discontinues early from the study

Subjects with GI AEIs will be asked to complete the PEESS v2.0 questionnaire (Franciosi, 2011) while the subject is symptomatic, at the End of Treatment visit, and then monthly for 6 months thereafter. Parents/caregivers will also complete the PEESS v2.0 as appropriate. It should be noted that the PEESS v2.0 was not designed to establish a diagnosis of EoE; the use of the PEESS v2.0 to monitor the clinical course of GI symptoms must be

considered exploratory. However, the PEESS v2.0 has shown content and construct validity (Franciosi, 2011; Martin, 2015) and holds promise for being a valuable tool to follow the clinical course of EoE or an EoE-like immune-mediated GI syndrome. The PEESS v2.0 could reveal trends toward symptomatic improvement or worsening that might otherwise go undetected.

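### Protocol 6.9.4 words more than 14 days of withheld AR101 as leaving the study; 4.4.1 item 7, with the same trigger, stops dosing only and exempts the 30-day GI hiatus

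*Protocol*

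**What the plan says.** Protocol 6.9.4 lists possible actions when a previously tolerated dose is no longer tolerated. One is to withhold AR101 temporarily, for an intercurrent adverse event or to judge tolerability. The limit is that "the duration of withholding study product may not exceed 14 consecutive days, or the subject will be discontinued from the study". The sentence has no exception. Table 10 in 6.9.5 sends once-daily maintenance subjects to the up-dosing procedures in 6.9.3 and 6.9.4, so the rule is not confined to up-dosing.

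Protocol 4.4.1 opens with "A subject who meets any of the following must discontinue dosing with AR101". Its item 7 covers daily regimens with 15 or more consecutive days missed for any reason, "with the exception of the voluntary 30-day hiatus for GI AEs". Section 8.1.4.2 plans for such subjects: one of its GI categories is a subject who develops chronic or recurrent GI events "at or before reaching the 20 mg dose level and resumes dosing after a 30-day dosing hiatus".

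On what follows, 4.4 says: "Following early discontinuation, subjects will return to the clinic to complete the End of Treatment visit". Section 3.2.7, for all pathways, says: "The End of Treatment visit will be followed by a 12-month observation period".

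For nondaily regimens, 6.9.5 option 2 allows about half of the 300 mg dose to be tried under supervision. It then says: "If not tolerated, the subject should be discontinued from the study".

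**The concern.** One event, AR101 withheld for more than two weeks, has two stated consequences. Under 4.4.1 the subject stops dosing, has the End of Treatment visit and is observed for a year. Under 6.9.4, read literally, the subject leaves the study. 6.9.4 also lacks the GI exception, so taken alone it would remove a subject partway through a hiatus that item 7 permits.

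The primary objective includes observation after the last dose, and Protocol 3.4.1 gives sustained clinical effect as the reason for the observation period. Subjects caught by the 6.9.4 rule had dosing withheld because of reactions or intercurrent events, so they are a selected group. If some sites ended their participation and others observed them for a year, observation would be incomplete in the subjects whose course after stopping is of most interest.

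**Working it through.** The plan gives no figure to reproduce. The check sets the rules side by side and bounds the effect.

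**Trigger.** In whole days, more than 14 consecutive days (6.9.4) equals 15 or more consecutive days (item 7). For daily regimens the triggers are the same.

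| | 6.9.4 bullet | 4.4.1 item 7 |
|---|---|---|
| Regimen | Up-dosing; once-daily maintenance through Table 10 | Daily regimens |
| Consequence | Study discontinuation | Stop AR101 dosing |
| Next step | Not stated | End of Treatment visit (4.4), then 12 months of observation (3.2.7) |
| GI hiatus | No exception | Exempt |

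**Is the difference only style?** The last bullet of 6.9.4 names further dosing and continuation in the study as two separate things, and 6.9.3 speaks of stopping study treatment when that is meant. A literal reading of the 14-day bullet is therefore reasonable, though not the only one.

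**GI hiatus.** Days 15 to 30 lie beyond the 6.9.4 limit: 30 − 15 + 1 = 16 of the 30 permitted days. Section 8.1.4.2 describes the hiatus only for subjects at or below the 20 mg level, so on that description this part concerns up-dosing, not 300 mg maintenance.

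**6.9.5 option 2.** Item 7 does not cover nondaily regimens. The mismatch here is only with 4.4 and 3.2.7.

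**Observation lost per affected subject** (365 days planned; contacts at months 3, 6, 9 and 12):
- Lower bound: 0 days, if the subject has the End of Treatment visit and then observation.
- Upper bound: only the 14-day minimum in 4.4.2 is kept and no adverse event is ongoing. 365 − 14 = 351; 351/365 = 96%; 4 of 4 contacts lost.
- Subjects who stop for chronic or recurrent GI events: 4.4.2 gives at least 6 months of monthly follow-up, taken as 183 days. 365 − 183 = 182; 182/365 = 50%; at most 2 of 4 contacts lost (months 9 and 12).

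**What the SAP does with that time.** SAP 9.1, 9.2.1 and 9.2.3 summarize events up to 30 days after the last dose; later events are listed. That is 365 − 30 = 335 days, or 335/365 = 92% of the observation year, that feeds listings only. This is an SAP convention, not a result of the 6.9.4 wording. SAP 10.1 summarizes the blinded food challenge at End of Treatment only. The summaries that depend on the year are mainly the exploratory Study Exit results for IgE/IgG4 (SAP 11.1) and skin prick test (SAP 11.2). For the skin prick test, change to End of Treatment is summarized as well.

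**The case against.** The strongest reply is that the protocol often writes study where it means dosing. Section 4.4 allows dosing to stop when continuing in the study would harm the subject, then gives the End of Treatment visit. Item 3 of 4.4.1 sits under a dosing rule yet speaks of continuing the study. Section 8.1.4.2 includes subjects who leave the study early and still schedules questionnaires at End of Treatment and monthly afterwards. Under 3.7, even a withdrawn subject has a further visit: "the subject will return to the clinic for an End of Treatment or Study Exit visit, as appropriate". An End of Treatment visit leads to observation. This stands. A reader might infer that the protocol directs these subjects out of observation; the documents do not support that. Loss of observation is one reading of one sentence.

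The GI omission is also softened. Item 7 states the exception, the paragraph after the 6.9.4 bullets refers chronic GI cases to 8.1.4.2, and the legends of Figures 5 and 6 define the abbreviation GI. The content of those figures is not reproduced in the text available, and they may carry the exception. The 14-day sentence would still need to agree with them.

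Option 2 of 6.9.5 is weaker evidence. It is one item in a non-exhaustive list, follows a required discussion with the medical monitor, and says should.

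Similar wording also remains in 3.1.1, 6.8.2, the end of 6.9.5 and the last bullet of 6.9.4. The first three offer leaving the study as an alternative to switching pathway, and the last names dosing and study continuation explicitly. None has a counterpart in 4.4.1 with the same trigger and a different consequence.

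Finally, a reader might infer that the planned outputs would hide any loss. They would not. SAP 8.1 tabulates reasons for stopping treatment, study and follow-up separately, and lists those reasons with dates of last visit and last contact, so the loss can be recovered subject by subject.

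**Conclusion.** The inconsistency is real and minor. For daily regimens, 6.9.4 and 4.4.1 item 7 share a trigger and state different consequences, and only item 7 carries the GI exception. Option 2 of 6.9.5 is a lesser mismatch with 4.4 and 3.2.7.

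Any loss of data rests on two assumptions: that some subjects had AR101 withheld beyond 14 days, or failed the half dose under option 2, and that their sites read the wording literally. The documents support neither a count nor a direction of bias, and the effect is zero if sites took the wording to mean stopping dosing. Even in the worst case the summarized outputs touched are mainly exploratory. Confidence is medium, because the unseen figures may settle the intended rule.

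**What to change.** In the 14-day bullet of Protocol 6.9.4, replace study discontinuation with: *discontinued from AR101 dosing (see 4.4.1 item 7), with the End of Treatment visit and follow-up observation per 3.2.7*, then add the item 7 exception, "with the exception of the voluntary 30-day hiatus for GI AEs". In 6.9.5 option 2, for consistency, change the consequence to *discontinued from AR101 dosing*. Leave the discretionary options to leave the study in 3.1.1, 6.8.2 and 3.7 as they are.

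The cost is two wording edits. Section 11.1 requires sponsor and ethics approval and regulatory submission for any amendment, so they belong in one made for other reasons. The only added burden is contacts that 3.2.7 and 3.2.8 already plan.

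If the protocol can no longer be amended, an optional step is to cross-tabulate completion of observation (Study Exit visit) by reason for stopping treatment, using the SAP 8.1 data. SAP Version 2 was written after database lock and is limited to Appendix A, so this table would be labelled post hoc under SAP 6.1.

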6.10 Treatment for Dosing Reactions: Pharmacological and Supportive Therapy

Treatment for allergic reactions during the study is guided by the type of symptoms and severity as determined by the investigator.

- Treatment for acute reactions should be provided according to the standard of allergy care, with an antihistamine and/or epinephrine, along with IV fluids, a beta-agonist (eg, albuterol, by inhaler or nebulizer), oxygen, and/or glucocorticosteroids, as indicated.
 - Many mild acute allergic reactions can be transient and self-limiting, requiring no therapeutic intervention. Others, however, may require treatment. Generally, for mild symptoms requiring treatment, the subject should receive antihistamines.
- Acute allergic reactions manifesting with moderate symptoms will generally require therapeutic intervention, although some, even moderate, symptoms may on rare occasion be so transient as to require no specific treatment. Generally, for moderate symptoms requiring treatment, the subjects should receive antihistamines and/or

- ARC008 Protocol Amend 6.0
- epinephrine, as indicated. If there is uncertainty as to the severity of the reaction, administering epinephrine would be considered the most appropriate course of action.
- Generally, severe symptoms will require treatment. This will usually consist of antihistamines and/or epinephrine, as indicated. If there is uncertainty as to the severity of the reaction, administering epinephrine would be considered the most appropriate course of action.

The procedures that should be implemented after treatment of a reaction to an AR101 dose during the study are summarized in Table 11. An explanation follows the table.

Table 11: Procedures Following Treatment of a Dosing Reaction

Treatment Given for Reaction	Procedures Following Treatment
≤ 2 doses of antihistamines	Continue dose escalation if in Initial Escalation / Up-Dosing Period
Epinephrine: > 2 doses either in clinic or at home	Subject returns to clinic, undergoes Early Discontinuation visit, discontinues treatment
Epinephrine: single dose given in clinic	 Stop dosing at clinic Reduce next dose by 2 dose levels and administer in clinic Continue biweekly escalation
Epinephrine required for a second consecutive time during, or after, 1 escalation attempt	 Reduce next dose by 2 dose levels and administer in clinic Reduced dose level continued for 6 to 8 weeks Escalation may be attempted after 6 to 8 weeks
Epinephrine required for a third consecutive time during an escalation attempt	Discontinue dosing Subject returns to clinic 14 days after last dose for Early Discontinuation visit
Epinephrine: single dose at home	Not counted in the total count of epinephrine uses unless severe anaphylaxis has occurred
	Reduce next dose by 1 or 2 dose levels and administer in clinic under medical supervision prior to resuming any dosing at home

• Antihistamines Given

If a subject receives 2 or fewer doses of antihistamines only, the dose escalation can be continued. If more than 2 doses of antihistamine, or epinephrine, or a combination of medications, is administered, then a different course of action is to be taken.

If symptoms during up-dosing at the study site or at home require > 2 doses of antihistamine alone or in combination with other medications (except epinephrine), reduce the next dose of study product by 1 or 2 dose levels and give it at the study site under medical supervision. If no symptoms occur at the reduced dose, continue up-dosing for the 2-week dosing interval.

ARC008 Protocol Amend 6.0

• Epinephrine – General Procedures

Any reaction to study product (in clinic or at home) that requires more than 2 doses of epinephrine will stop all further dosing of study product for the individual. The subject will be asked to return 14 days following the last dose of study product for an Early Discontinuation visit (Section 4.4).

• Epinephrine – Single Dose Administered at Clinic

If a single administration of epinephrine is required during, or after, a dose escalation in the clinic, no further dosing of study product is to occur at that visit. The next dose of study product is to be reduced by 2 dose levels and administered at the study site, but biweekly dose escalation should continue.

If a single administration of epinephrine is required for a second consecutive time during or after 1 escalation attempt, the dose should be reduced by 2 dose levels and the same dose level continued for 6 to 8 weeks. After 6 to 8 weeks at the reduced dose, an escalation may be attempted in the clinic.

If a single administration of epinephrine is required for a third consecutive time during an escalation attempt, no further dosing should be attempted and dosing will be discontinued. Subjects will be asked to return 14 days following their last dose of study product for an Early Discontinuation visit (Section 4.4).

• Epinephrine – Home

If a single administration of epinephrine is given during dosing at home, this epinephrine use is not counted as one of the uses described above unless severe anaphylaxis occurred at home. Administration of epinephrine outside of the clinic should be followed immediately by the subject being taken to the nearest emergency department. The next dose of AR101 is to be reduced by 1 or 2 dose levels and administered in the clinic under medical supervision prior to resuming any dosing at home.

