• Mild symptoms that indicate lack of tolerability: If mild symptoms other than oral/pharyngeal pruritus occur with the first dose at a new dose level and the dose is assessed as not tolerated, the action taken should be to have the subject return the next day for dosing at the last tolerated dose (ie, a 1-step dose reduction) under medical supervision at the study site (if the subject is unable to return on the day specified, the investigator may initiate an approximate 1 dose-level reduction at home, with the subject coming to the study site at the earliest date possible).

If the reduced dose is *assessed as tolerated*, the subject is to continue on that daily home dose for the ensuing 2 weeks. (See Section 6.9.4 and Section 6.9.5 for actions to be taken if symptoms develop during home-dosing.) If the reduced dose is again *assessed as not tolerated*, the subject is to return the next day for supervised dosing at

- a 1- or 2-step reduction in dose (per investigator judgment, based on severity of reaction) at the study site. If this further reduced dose is *assessed as tolerated*, the subject will continue at that dose level for daily home-dosing over the ensuing 2 weeks. If, however, the reduced dose is *assessed as not tolerated*, the subject will discontinue study treatment.
- Moderate symptoms (these indicate lack of tolerability, with rare exceptions): On rare occasions, a transient, self-limited (requiring no intervention and resolving completely) symptom of moderate intensity occurring in a single organ system may be assessed as tolerated. Typically the symptom would be subjective only. Any dose associated with moderate symptoms and assessed as tolerated must be accompanied by a brief explanation in the CRF as to why the dose was considered tolerated; (see Section 6.8.2, for moderate symptoms assessed as tolerated): If moderate symptoms occur with the first dose at a new dose level, except for rare instances, the dose will be assessed as not tolerated. The action taken should be to have the subject return the next day for dosing at the last tolerated dose under medical supervision at the study site. If this reduced dose elicits no allergic symptoms (ie, is well tolerated), the subject will continue on that daily home dose level for an additional 2 weeks.

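### For one epinephrine dose given in the clinic at a dose that is not the first at a new level, Table 11 and Section 6.9.4 of the protocol give different dose reductions and hold periods

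*Protocol*

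**What the plan says.** All references are to the protocol.

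- **Section 6.10, text.** For one epinephrine administration needed around a dose escalation in the clinic: "The next dose of study product is to be reduced by 2 dose levels and administered at the study site". Escalation every two weeks goes on. After one administration at home, the cut is 1 or 2 levels.
- **Table 11, in-clinic row.** "Reduce next dose by 2 dose levels and administer in clinic", again with two-weekly escalation continuing. This row is not limited to an escalation dose.
- **Table 11, home row.** "Reduce next dose by 1 or 2 dose levels and administer in clinic under medical supervision prior to resuming any dosing at home".
- **Section 6.9.4** (up-dosing, after the first dose at a level). "Reducing dose by 1 or 2 dose levels and maintaining the reduced dose level for 2- to 4-week period before attempting dose re-escalation". One of the listed triggers is "if a single dose of epinephrine has been administered to treat a dosing reaction", with no setting given. The section calls this its default response to a dose that was not tolerated.
- **Section 6.9.3** (first dose at a new level). For a mild reaction judged not tolerated: "have the subject return the next day for dosing at the last tolerated dose (ie, a 1-step dose reduction) under medical supervision". The moderate branch also returns the subject to the last tolerated dose. Neither branch mentions epinephrine. The severe branch with 0 to 1 epinephrine dose cuts by 2 levels and holds for 2 to 4 weeks.
- **Cross-references.** Sections 6.9.3, 6.9.4 and 6.9.5 each refer dose adjustment after epinephrine to 6.10. Table 10 sends reactions during daily maintenance to 6.9.3 and 6.9.4.

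**The concern.** The same event can meet two instructions. A subject may receive one epinephrine dose in the clinic at a supervised dose that does not open a new level. Examples are the End Up-Dosing visit, a repeat dose under observation, and a daily-regimen maintenance visit. Table 11 fixes the cut at 2 levels and keeps the two-weekly schedule. Section 6.9.4 leaves 1 or 2 levels open and allows a hold of up to 4 weeks. The 6.10 text does not settle the matter, because its own in-clinic rule is worded for dose escalations only.

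What is at stake is the size of the next supervised dose after a reaction that needed epinephrine, and whether sites handle that event alike. The study is descriptive, so no hypothesis test or sample size is affected.

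**Working it through.** **Step 1: check the ladder.** The Pathway 3 levels in Table 5 are 3, 6, 12, 20, 40, 80, 120, 160, 200, 240 and 300 mg. The percent increase is 100 × (dose ÷ previous dose − 1). This gives 100, 100, 67, 100, 100, 50, 33, 25, 20 and 25, which matches the table's own column. The documents state no figure for the gap between the two cuts.

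**Step 2: set the instructions side by side for one epinephrine dose.**

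| Source | Setting stated | Cut | Hold |
|---|---|---|---|
| 6.10 text | Clinic, dose escalation | 2 levels | Two-weekly escalation continues |
| Table 11 | Clinic, any dose | 2 levels | Two-weekly escalation continues |
| 6.10 text and Table 11 | Home | 1 or 2 levels | Not stated |
| 6.9.4 | Not stated | 1 or 2 levels | 2 to 4 weeks |
| 6.9.3, severe, 0 to 1 dose | Clinic, first dose at a level | 2 levels | 2 to 4 weeks |
| 6.9.3, mild or moderate | Clinic, first dose at a level | 1 level, epinephrine not mentioned; refers to 6.10 | 2 weeks |

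Section 6.9.4 cannot be read as a home-only rule. The item that names epinephrine also covers a dose observed at the study site, the section encourages observed dosing, and Table 10 routes daily maintenance reactions to it.

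**Step 3: size of the gap.** For a reaction at level k, the ratio is the dose after a 1-level cut divided by the dose after a 2-level cut, d(k−1) ÷ d(k−2). It can be computed within Table 5 from 12 mg upward.

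| Reaction at (mg) | 1 level down | 2 levels down | Ratio |
|---|---|---|---|
| 12 | 6 | 3 | 2.00 |
| 20 | 12 | 6 | 2.00 |
| 40 | 20 | 12 | 1.67 |
| 80 | 40 | 20 | 2.00 |
| 120 | 80 | 40 | 2.00 |
| 160 | 120 | 80 | 1.50 |
| 200 | 160 | 120 | 1.33 |
| 240 | 200 | 160 | 1.25 |
| 300 | 240 | 200 | 1.20 |

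For daily maintenance at 300 mg the relevant figure is the last row, 1.20. On the Pathway 2 repeat up-dosing ladder (Table 4), with both cuts inside the table, the range is 1.20 to 1.50.

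**Step 4: Pathway 5, under an assumption.** The rows of Table 6 are not legible in the text available. Suppose its ladder is 1 mg followed by the Table 5 levels. That is 12 levels × 2 weeks = 24 weeks, which agrees with the stated 24-week minimum. The ratio after a reaction at 6 mg would then be 3 ÷ 1 = 3.00, and the other ratios would be as above.

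**Step 5: timing.** One extra level down costs about 2 weeks of re-escalation. The slack in up-dosing is 52 − 22 = 30 weeks in Pathway 3 and 40 − 24 = 16 weeks in Pathway 5.

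**The case against.** The strongest reply is that the protocol already names the governing section. Sections 6.9.3, 6.9.4 and 6.9.5 all refer adjustment after epinephrine to 6.10, and the up-dosing visit sections cite 6.10 when epinephrine delays escalation. Section 6.9.4 is mainly about home dosing, and its range of 1 or 2 levels equals the 6.10 home rule. It offers possible actions subject to clinical judgment and is worded as a general rule. A site that cuts by 2 levels and re-escalates after 2 weeks satisfies both texts.

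Most of this stands, and it makes the point narrow. It does not remove it. Compliance runs one way only: a 1-level cut, or a 4-week hold, satisfies 6.9.4 but not Table 11. Section 6.9.4 gives its own instruction for the event that it refers elsewhere, and nothing says that the referral overrides it.

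Two stronger readings are tempting, and the documents do not support them. A reader might infer that 6.9.3 orders a 1-level cut after epinephrine. It does not. Its mild and moderate branches are silent on epinephrine, its opening text refers to 6.10, and its only branch for 0 to 1 epinephrine dose also says 2 levels. What remains is a risk of misreading. Section 6.8.2 treats a mild reaction needing one epinephrine dose as not tolerated, and 6.10 foresees epinephrine for moderate reactions, so both can land in the 1-step branches. A reader might also infer that the discrepancy changes who is discontinued for failing up-dosing. No figure supports that, and about 2 weeks is small against 16 to 30 weeks of slack.

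**Conclusion.** The inconsistency is real but confined to one situation: a single epinephrine dose given in the clinic at a supervised dose that is not the first at a new level, daily maintenance included. There, Table 11 and 6.9.4 differ on both the cut and the hold. A site using the 1-level option in 6.9.4 would give a next dose 1.2 to 2.0 times the Table 11 dose on the Table 5 ladder. The factor reaches 2.0 only after reactions at 12, 20, 80 and 120 mg. It is 1.5 or less from 160 mg up, and 1.2 at the 300 mg maintenance dose. A three-fold gap in Pathway 5 rests on the assumed Table 6 ladder. Section 6.9.3 is a clarity gap and does not contradict 6.10 on the size of the cut. The discrepancy is worth correcting because it concerns dosing straight after an epinephrine-treated reaction. No view is taken here on which reduction or hold is right.

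**What to change.** 1. Reconcile 6.9.4 with the 6.10 text and Table 11, so that one reduction and one hold period apply to each defined event.
2. State in each place the setting that the rule covers: clinic or home, and escalation dose or other dose. Bring the 6.10 text and the Table 11 in-clinic row to the same scope.
3. Repeat within the mild and moderate branches of 6.9.3 that 6.10 governs once epinephrine has been given. Align the hold in the severe branch with 6.10 as well.

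The reduction and the hold period are for the sponsor's clinical team to choose. The cost is a wording change at the next amendment or a clarification letter to sites. No analysis needs to change.
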